### **Data Analysis & Statistical Considerations**

Descriptive statistics for each treatment group will be computed for patient demographic and characteristic variables. Since our randomization scheme will have balanced the age effect between treatment groups, we anticipate the demographic and patient characteristic variables will be balanced across groups. For the continuous outcome measures (primary and most of secondary outcomes), we will conduct two-sample t-test to test the outcome difference (e.g., total OME difference) between treatment groups. For categorical outcomes (e.g., PACU side effects and adverse events), chi-square or Fisher exact tests will be applied as appropriate. Considering this is a pilot study for dose finding, we will relax the significance threshold to 0.1 for the interim analysis. Using the primary outcome, total OME/kg as an example, a two-sample t-test will be performed for comparing total OME difference between 20 methadone (0.1mg/kg) treated patients to 10 controls based on significance threshold of 0.10. If methadone showed significant effect on the outcome measure, the higher dose arm (0.15 mg/kg age ideal body weight) will be pursued. In the final analysis, similarly, two-sample test

will be used to test the total OME difference between methadone and control groups for both dose levels. To correct for multiple testing, the significance threshold in the final analysis will be set at 0.025. If there are covariates showing significant difference between treatment groups, we will perform multivariable linear regression analysis to test the treatment effect after adjusting for one selected covariate and examine if the treatment effect remains the same as that found in the two-sample t-test. The reason to restrict to one covariate in the model was to avoid model overfitting considering there will be only 20 samples per group. Similar analysis strategy will be applied to other outcome measures.

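### The adjusting covariate is chosen by testing for baseline imbalance, which will seldom pick age, and the plan does not say whether the regression or the t-test decides

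*Combined protocol and SAP*

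**What the plan says.** All of this is in the combined protocol and SAP, Data Analysis & Statistical Considerations, unless noted.

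- The main analysis of continuous outcomes is unadjusted: "we will conduct two-sample t-test to test the outcome difference (e.g., total OME difference) between treatment groups".
- Thresholds are attached to that test. At the interim, "we will relax the significance threshold to 0.1 for the interim analysis". At the end, "To correct for multiple testing, the significance threshold in the final analysis will be set at 0.025".
- Adjustment is conditional: "If there are covariates showing significant difference between treatment groups, we will perform multivariable linear regression analysis to test the treatment effect".
- The regression is limited to one covariate and is set beside the t-test: "after adjusting for one selected covariate and examine if the treatment effect remains the same as that found in the two-sample t-test".
- The limit has a stated reason: "The reason to restrict to one covariate in the model was to avoid model overfitting considering there will be only 20 samples per group".
- A similar strategy is to be used for the other outcome measures.

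The section lists no candidate covariates. It gives no significance level for the baseline tests, no way to choose if several variables differ, and no statement of which result prevails.

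Study Interventions sets up blocked randomisation in three age groups because pain tolerance may differ with age. Age is not named as a covariate in any analysis. Unblinding Procedures places the final unblinding after all patients have finished.

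**The concern.** A covariate is worth adjusting for when it predicts the outcome. The plan asks instead whether it differs between arms. Under randomisation such a difference is chance, so the rule can bring in a variable with no bearing on opioid use and leave out one that matters but happens to be balanced.

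Age shows this best. It is the one factor the plan gives a reason to think prognostic, and the stratified blocks are there to balance it. A trigger based on imbalance will therefore rarely select it.

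The choice is also open to discretion. A between-arm test cannot be run without the allocation, so the covariate is selected when the outcome data can be seen by arm. That timing is an inference; the plan does not say it in so many words. If the adjusted and unadjusted p-values then fall on opposite sides of 0.025, the plan says only that they will be compared.

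At stake are a clear reading of the two final dose comparisons and whatever precision a prognostic baseline variable could give.

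**Working it through.** **1. The plan's own power figures.** Inputs from the power calculation paragraph: SD 0.3; final 20 vs 20, difference 0.31, alpha 0.025; interim 20 vs 10, difference 0.3, alpha 0.1. Sidedness is not stated. The method is the equal-variance t-test with noncentral-t power, two-sided.

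- Final: noncentrality = 0.31 / (0.3 × √(1/20 + 1/20)) = 3.27; critical value on 38 df = 2.33; power = 0.8205 (stated 82%).
- Interim: noncentrality = 0.3 / (0.3 × √(1/20 + 1/10)) = 2.58; critical value on 28 df = 1.70; power = 0.809 (stated 80%).

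Both reproduce. One-sided versions give 0.89–0.90, so the plan used two-sided tests.

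**2. How often the trigger fires.** The plan gives neither the number of baseline variables k nor the test level. Assume independent variables tested at 0.05. The chance of at least one significant difference is 1 − 0.95^k.

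- k = 1: 5%; k = 3: 14%; k = 6: 1 − 0.735 = 26.5%; k = 10: 40%.
- For k = 6, at least one of the two final comparisons, which share controls, triggers in about 43% of trials (simulated).

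**3. How often the two tests disagree.** Simulated 20 vs 20 comparisons with six independent baseline variables, two of them correlated r = 0.3–0.4 with the outcome, the most imbalanced one selected, difference 0.31, alpha 0.025.

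- Given a trigger: about 14%.
- Over all comparisons: 0.265 × 0.14 = 0.037, about 4%.
- Other assumptions move this. One variable with r = 0.5: 0.051 × 0.285 = 1.4%. Eight variables, each with r = 0.3: 0.341 × 0.179 = 6.1%.

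**4. Type I error** (nominal 0.025; one to eight variables, correlations 0 to 0.5).

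- If either significant result may be claimed: about 0.026–0.029.
- If the regression replaces the t-test when triggered: about 0.013–0.025, at or below nominal.

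**5. Power with two covariates named in advance**, each with correlation r with the outcome, 20 vs 20, difference 0.31, alpha 0.025 (simulated; r is an assumption).

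| r (each) | Two named covariates | Unadjusted t-test |
|---|---|---|
| 0 | 79% | 82% |
| 0.1 | 80% | 82% |
| 0.2 | 83% | 82% |
| 0.3 | 87–88% | 82% |
| 0.4 | 93% | 82% |

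The false-positive rate of the two-covariate model is about 2.4–2.6%. If the plan's conditional regression replaced the t-test when triggered, power would be about 81–82% at r = 0.3–0.4, so the conditional adjustment adds no power.

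**6. Cost of a useless covariate.** With 40 children, one irrelevant term inflates the variance of the treatment effect by an expected factor of 37/36 = 1.028, about 3%.

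**The case against.** The strongest reply is that a hierarchy can be read from the text. The t-test comes first, carries both thresholds and is the only test that was powered. The regression is conditional and is compared back to it, which is how one describes a robustness check. This largely stands. A reader might infer that the plan leaves its conclusion to free choice after unblinding, and that goes too far. What remains is that the plan never calls the regression supportive; it describes it as testing the treatment effect.

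A reader might also infer that the procedure inflates false positives. It does not to any extent that matters: even claiming whichever result is significant takes 0.025 only to about 0.026–0.029.

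Nor do the documents show that precision is certainly being lost. They give no correlation between any baseline variable and opioid use. The gain from adjustment is clear at r = 0.3 or more, negligible at 0.2, and a small loss below that.

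Finally, limiting the model to one covariate is a reasoned choice in a small pilot and is not an error in itself. The objection does not rescue the way that one covariate is chosen.

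**Conclusion.** The selection rule is unsound and cheap to replace. It chooses covariates by chance imbalance, with the allocation known, and will seldom reach age. The deciding analysis is implied but not stated.

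The practical size is modest. With six independent baseline variables tested at 0.05, about 26% of comparisons would trigger adjustment. About 4% of all comparisons at the 0.31 effect would end with conflicting results (1.4% to 6.1% across the assumptions tried). Naming two covariates in advance would change power from 82% by between a loss of 2–3 points (r = 0 to 0.1) and a gain of about 11 points (r = 0.4). The number of variables, the baseline test level and the correlations are all assumptions, because the plan gives none of them. This is a change that should be made; it does not threaten the validity of the trial.

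**What to change.** Delete the significance trigger. Before the interim unblinding, write into the SAP:

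- the covariates: age first, as the randomisation stratifier, and at most one other baseline variable expected to predict opioid use;
- the form in which age enters (continuous uses one degree of freedom, the three age groups use two);
- that these covariates are included whatever their balance, for the primary outcome and the other continuous outcomes;
- which result is decisive at 0.025. The adjusted result is preferable, with the t-test reported as supportive. If the sponsor prefers to keep the t-test decisive, one sentence saying so removes the ambiguity.

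Present baseline characteristics descriptively, without between-arm p-values. If the adjusted result is made decisive, add a line to the power paragraph noting that the 82% refers to the unadjusted test.

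The cost is SAP wording only, with no extra patients or data. The statistical price is about 3% in variance per single-term covariate that proves irrelevant, or 2–3 points of power if two such covariates are both useless.

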#### **Design & Procedures**

Study Design: Single center, randomized, double blind, parallel-group dose escalation investigation. All patients will receive standard monitoring for anesthesia and postoperative care. Surgical and anesthesia care (except for intraoperative opioid management) are not altered for study purposes. Subjects are randomized 2:1 to either long-duration (methadone) or short-duration opioid (fentanyl, hydromorphone). The use of any short acting opioid (ie: fentanyl, hydromorphone or both) is considered the control group and total dose, timing of administration, frequency of administration, and dose per administration of either/both short acting opioids will be administered at the discretion of the anesthesiologist as per standard of care practice. Because methadone analgesia for pediatric tonsillectomy has not previously been studied, this pilot study will use escalating dose groups to determine the optimal dose for this procedure. In order to achieve this, our trial design will include two periods. In the first period, we will randomly assign 20 patients to methadone 0.1 mg/kg and 10 patients to typical shortduration opioid (controls). An interim analysis will be conducted to determine if we should escalate to the higher dose of methadone. Methadone dose escalation to 0.15mg/kg age ideal body weight will occur if there is no difference in non-methadone PACU opioid use and no increased adverse events. If proceeding to the second period, we will recruit 20 patients for 0.15 mg/kg methadone and 10 patients as controls. Sample size for this pilot investigation was based on prior studies.

Defining an optimal dose of methadone is a crucial aim of this study, which will allow for future investigations, but is not a primary or secondary outcome. The dose finding nature of this study requires interim assessments after each methadone dose cohort. After the first 20 methadone subjects at 0.1mg/kg age ideal body weight, there will be a planned partial analysis of PACU opioid use. Methadone dose escalation to 0.15mg/kg age ideal body weight will occur if there is no difference in non-methadone PACU opioid use and no increased adverse events. Sample size for this pilot investigation was based on prior studies.

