#### Subject Recruitment and Compensation

Patients will be screened and properly identified by the principal investigator or member of the clinical research team assigned to the study through IRB-approved review of the surgical schedule. An IRB-approved phone call may be conducted to introduce the study or patients may be approached on the day of surgery allowing sufficient time for explanation, questions and answers. If interested, legal guardians may provide consent for the study via an IRB approved electronic Informed Consent Form (ICF) in advance or paper consent may be obtained on the day of surgery. For patients 12 years or older, patient assent for enrollment in the study will also be obtained.

Goal recruitment is 60 patients to complete the study. Subjects will be compensated a \$10 gift card (mailed) for the time and effort to complete 1-7d daily surveys and the phone call on day 30 following surgery.

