#### **Study Interventions**

Study Intervention and Randomization: Subjects in each cohort will be randomized 2:1 methadone to short acting opioid using randomization tables generated by The Biostatistics Group within the Department of Anesthesia. Each subject is assigned the next number. To consider children in different age may have different pain tolerance, we will balance the treatment groups by age. That is, we will generate a set of blocked randomization numbers for three age groups, 3-6, 7-12, and 13-17 years old. Anesthesia providers receive a sealed envelope or email with Group (drug) assignment, group-specific instructions, and are advised on study procedures. To ensure full double-blinding, subjects, investigators, and study team members evaluating patients will be blinded to drug treatment. The rationale for 2:1 randomization is to achieve the same sample size for each group since we anticipate 2 methadone cohorts, thus final groups (methadone 0.1 mg/kg, methadone 0.15 mg/kg, controls) would each have 20 subjects.

As clarified above, the use of a short duration opioid in this specific study population (tonsillectomy 3-18 year olds) is a standard of care procedure. Methadone is standard of care in pediatric cardiac surgery, pediatric spine surgery and precuts excavatum surgery (3-18 year olds). Not counting the randomization, the dosing and administration of all 3 of these drugs (methadone, fentanyl, hydromorphone) are in line with standard of care practices for pediatric population of between 3 and less than 18 years and are routinely used both in and out of the operating room environment.

Regarding the clinical study of an investigational drug that would be IND exempt, the following ARE true for this study (see below):

- The investigation of a drug that is lawfully marketed in the US and the following 5 criteria are met:

the study is not designed to support approval of a new indication or change in labelling: No new indications sought

the study does not intend to support significant change in advertising of the product: No new advertising sought

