Power calculation: Two-sample t-test with an assumption of equal variance between groups was used to estimate statistical power. For the interim analysis based on 20 methadone 0.1mg/kg cases and 10 controls, assuming standard deviation (SD) total OME as 0.3, our proposed sample size will have 80% power to detect 0.3 OME difference at the significance level (alpha) of 0.1. Assuming we can move forward to the higher dose cohort, the final analysis will include two tests to compare 20 cases vs. 20 controls for each methadone dose level. In this scenario, assuming the same OME variability of SD=0.3 and the reduced alpha level to 0.025, our proposed sample size (N=20/group) can detect the 0.31 OME difference between methadone and control groups with 82% power, a similar effect size as the interim analysis. The detectable mean difference will increase if the OME variability (SD) increases.

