#### **Unblinding Procedures:**

Emergency Unblinding is appropriate in the unlikely situation of a medical emergency (as determined by the PI or treating physicians, APPs) where knowledge of the treatment allocation is likely to have a significant effect on the clinical management of the enrolled subject and would be instrumental in immediate treatment decisions. In an emergency, it may not be feasible to obtain prior approval from the PI. In this case, after the subject is successfully unblinded, there must be clear documentation explaining why unblinding was necessary. The PI, IRB, and Research Practice Manager will be notified as soon as possible.

Accidental Unblinding: If a subject is accidentally unblinded, clear documentation of events must be recorded, as well as communication with the PI and Research Practice Manager. The treatment assignment must not be revealed to any other members of the study staff, pharmacy staff, or to the subject, unless written approval from the study sponsor is obtained. Every effort should be made to maintain what remains of the blind. In this case, a protocol deviation should be reported to the IRB of record.

Interim Analysis: Patients will be unblinded for the interim analysis by a member of the Department of Biostatistics. The interim analysis will determine if a dose escalation is indicated. Once the partial analysis is complete, the study we resume either at the same dose of

methadone (0.1mg/kg age ideal body weight or an increased dose 0.15mg/kg age ideal body weight).

Primary and secondary endpoint data collection will occur while the study team is blinded with exception of the interim analysis. Once all patients have completed the all parts of the study, final unblinding will occur.

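### The two escalation rules point in opposite directions, and the 82% final power is stated for the escalated trial without allowing for the interim decision that selects it

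*Combined protocol and SAP*

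**What the plan says.** All references are to the combined protocol and SAP.

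- **Final power** (Data Analysis & Statistical Considerations, power calculation): "Assuming we can move forward to the higher dose cohort, the final analysis will include two tests to compare 20 cases vs. 20 controls" at each methadone dose level. With SD 0.3 and alpha 0.025, "our proposed sample size (N=20/group) can detect the 0.31 OME difference between methadone and control groups with 82% power".
- **Escalation, first statement** (Data Analysis & Statistical Considerations): the interim t-test compares 20 methadone patients with 10 controls at 0.10, with total OME/kg as the worked example. "If methadone showed significant effect on the outcome measure, the higher dose arm (0.15 mg/kg age ideal body weight) will be pursued".
- **Escalation, second statement** (Design & Procedures): "Methadone dose escalation to 0.15mg/kg age ideal body weight will occur if there is no difference in non-methadone PACU opioid use", provided adverse events are not increased. No test or alpha is attached to this rule there.
- **Who is in the final groups**: Design & Procedures has 20 patients on 0.1 mg/kg and 10 controls in the first period. Then "If proceeding to the second period, we will recruit 20 patients for 0.15 mg/kg methadone and 10 patients as controls". Study Interventions adds: "thus final groups (methadone 0.1 mg/kg, methadone 0.15 mg/kg, controls) would each have 20 subjects". The 20 final controls are therefore 10 interim controls plus 10 new ones, and the final 0.1 mg/kg group is the interim group.
- **No escalation** (Unblinding Procedures): "Once the partial analysis is complete, the study we resume either at the same dose of" methadone or at the increased one. No section says what is recruited or tested if the dose stays the same. The only total is "Goal recruitment is 60 patients to complete the study".

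**The concern.** There are two linked problems.

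First, the rules conflict. If PACU opioid use is clearly lower on methadone at the interim, the Data Analysis rule, applied to that outcome, pursues the higher dose and the Design & Procedures rule does not. If no difference is seen, the decisions are reversed. The biostatistician who unblinds the interim data cannot apply both.

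Second, the final power is given for a trial that has escalated, yet it is computed as if escalation were unrelated to the data. Patients who helped to trigger escalation are tested again at the end. Selecting on a significant result pushes the later estimates up and raises power given escalation. Selecting on a non-significant result does the reverse. The direction of the departure from 82% therefore depends on which rule is meant. The plan says nothing about either effect, although Design & Procedures treats finding the dose as central and expects later studies to build on it.

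**Working it through.** **1. Reproduce the stated figures.** Inputs from the power calculation: SD 0.3, equal variances, t-test. Sidedness is not stated.

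- Final test: SE = 0.3 × √(1/20 + 1/20) = 0.0949. Noncentrality = 0.31 / 0.0949 = 3.268, 38 df. Two-sided alpha 0.025 gives critical t = 2.334 and power 82.0% (stated 82%). A one-sided test would give 89.0%, so two-sided was intended.
- Interim test: SE = 0.3 × √(1/20 + 1/10) = 0.1162. For a difference of 0.3, noncentrality = 2.582, 28 df. Two-sided alpha 0.10 gives critical t = 1.701 and power 80.9% (stated 80%). For 0.31 it is 83.1%.

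**2. How strongly the final estimates depend on the interim one.** The variance of a mean is 0.09/n: 0.0045 for 20 patients and 0.009 for 10. The interim difference has variance 0.0045 + 0.009 = 0.0135. The interim controls carry weight one half in the final control mean.

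- 0.1 mg/kg: covariance = 0.0045 + 0.5 × 0.009 = 0.009; slope = 0.009 / 0.0135 = 2/3.
- 0.15 mg/kg (through shared controls only): covariance = 0.5 × 0.009 = 0.0045; slope = 1/3.

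**3. Size of the bias at a true 0.31 for both doses** (normal approximation). The interim significance cut-off is 1.701 × 0.1162 = 0.198, that is z = (0.198 − 0.31) / 0.1162 = −0.967. There the normal density is 0.250 and the lower-tail probability 0.167.

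- Given significance, the interim difference is too large by 0.1162 × 0.250 / 0.833 = 0.035. Multiplying by 2/3 and 1/3 gives +0.023 and +0.012.
- Given non-significance, it is too small by 0.1162 × 0.250 / 0.167 = 0.174, giving −0.116 and −0.058.

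**4. Simulation** (400,000 trials; interim 20 vs 10 at two-sided 0.10; final 20 vs pooled 20 controls at two-sided 0.025). Assumptions: same endpoint at interim and final, no adverse-event stop, no difference read as p>=0.10, true 0.31 at both doses.

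| Escalate if | Trials escalating | Power given escalation, 0.1 / 0.15 mg/kg | Mean estimates |
|---|---|---|---|
| Interim significant | 83% | 92% / 86% | 0.333 / 0.322 |
| Interim not significant | 17% | 33% / 63% | 0.197 / 0.254 |

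The estimates agree with step 3.

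**5. Sensitivity.**

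- *Different endpoint.* The documents give no correlation between PACU opioid use and total OME. Assume the same difference and SD for both. Power given escalation under the no-difference rule is then 48% / 68% at correlation 0.8, 64% / 74% at 0.5, and about 82% for both doses at 0.
- *Smaller effect at 0.1 mg/kg.* With 0.31 at 0.15 mg/kg and 0 / 0.10 / 0.15 / 0.20 at 0.1 mg/kg, the 0.15 mg/kg test under the no-difference rule has 83 / 79 / 77 / 74% power. At 0 its mean estimate is 0.31, so there is no bias.
- *Same cases, significant-effect rule.* If only results favouring methadone escalate, 0.15 mg/kg power is 97 / 94 / 92 / 90%. If escalation is two-sided, the first figure falls to about 75%, because escalation then also follows results against methadone.

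**6. No effect at either dose.** Under the significant-effect rule about 10% of trials escalate. The false-positive rate given escalation is about 20% / 6%. The probability of escalating and rejecting is 0.10 × 20% = 2.0% and 0.10 × 6% = 0.6%. Under the no-difference rule (about 90% escalate) the joint probabilities are about 0.5% and 1.9%. All are below 2.5%.

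**The case against.** The best defence is that 82% is a conventional fixed-sample figure, correctly calculated. On this reading the opening clause of the power sentence only says when 20 per group will exist and makes no claim about power given an interim p-value. That is a fair reading, and nothing here is an arithmetic error. Under the significant-effect rule, the only one with a stated test and alpha, 82% is conservative at the design difference. The overestimation there (0.023 and 0.012) is at most about a quarter of the final standard error of 0.095. This stands, and it limits the severity.

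Three stronger readings are tempting, and the documents do not support them.

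- *That the trial really has 33% / 63% power.* This needs the no-difference rule, a p>=0.10 reading, identical endpoints and a full 0.31 already present at 0.1 mg/kg. It describes the 17% of trials in which the interim test missed a real effect.
- *That type I error is inflated to 20%.* That rate is conditional on escalation. The joint rates stay below the 2.5% per-test level under both rules.
- *That the final estimates are always biased, or that overall power can be quoted.* With no effect at 0.1 mg/kg, the no-difference rule leaves the 0.15 mg/kg estimate unbiased. Overall power for 0.1 mg/kg needs an analysis of the same-dose branch, and the plan does not give one.

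It can also be said that the root problem is the pair of contradictory rules. That is largely so, but reconciling them does not remove the reuse of interim patients. It settles which way the selection works.

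**Conclusion.** The concern holds in limited form, at minor to moderate severity. The opposite escalation rules are a contradiction on the face of the plan and need no assumptions to establish. The 82% is correct for a stand-alone test, but it is attached to a case selected by data that the final tests use again. How far power given escalation departs from 82%, and in which direction, cannot be settled until one rule, endpoint and test are fixed. The simulated figures rest on normal outcomes with SD 0.3, no adverse-event stop and the stated reading of no difference. The figures for the no-difference rule depend most on these choices. The 0.15 mg/kg comparison is less exposed than the 0.1 mg/kg one, since it is linked to the interim only through 10 shared controls.

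**What to change.** 1. Reconcile the escalation rules in Design & Procedures and in Data Analysis & Statistical Considerations, naming the endpoint, test (including sidedness) and alpha. State what is recruited and tested if the study resumes at the same dose, as Unblinding Procedures allows. This review takes no position on which rule is right.
2. In the power calculation, label 82% as the power of a stand-alone 20 vs 20 t-test that does not account for the interim decision. Once the rule is fixed, add simulated power per dose given escalation over a range of true 0.1 mg/kg effects (for example 0 to 0.31). If the interim and final endpoints differ, vary their correlation as well.
3. State that after escalation the 0.1 mg/kg estimate, and through the shared controls the 0.15 mg/kg estimate, can be affected by interim selection.
4. Optionally, report 0.15 mg/kg against second-period controls only (20 vs 10) as a sensitivity estimate. The interim decision does not affect it, but it has about 62% power at 0.31 (noncentrality 0.31 / 0.1162 = 2.668, 28 df, two-sided alpha 0.025).

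The cost is one simulation and a few sentences, with no extra patients. The sponsor would report a range of power figures in place of one.
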